## **7.6. Treatment Compliance**

- When participants are dosed at the site, they will receive study treatment directly from the investigator or designee, under medical supervision. The date and time of each dose administered in the clinic will be recorded in the source documents. The dose of study treatment and study participant identification will be confirmed at the time of dosing by a member of the study site staff other than the person administering the study treatment. Study site personnel will examine each participant's mouth to ensure that the study treatment was ingested.

## **7.7. Concomitant Therapy**

Any medication or vaccine (including over-the-counter or prescription medicines, vitamins, and/or herbal supplements) that the participant is receiving at the time of enrollment or receives during the study must be recorded along with:

- reason for use
- dates of administration including start and end dates
- dosage information including dose and frequency

The Medical Monitor should be contacted if there are any questions regarding concomitant or prior therapy.

Participants must abstain from taking prescription or nonprescription drugs (including vitamins and dietary or herbal supplements) within 7 days (or 14 days if the drug is a potential enzyme inducer) or 5 half-lives (whichever is longer) before the start of study treatment until completion of the follow-up visit, unless, in the opinion of the investigator and sponsor, the medication will not interfere with the study.

Paracetamol, at doses of  $\leq 2$  grams/day, is permitted for use any time during the study. Other concomitant medication may be considered on a case-by-case basis by the Investigator in consultation with the Medical Monitor if required.

## 7.8. Treatment after the End of the Study

Participants will not receive any additional treatment from GSK, or with GSK2983559, after the completion of the study because only healthy participants are eligible for study participation.

## 8. DOSE ESCALATION CRITERIA

### 8.1. PK criteria for GSK2668176

Due to the non-tolerated high dose of 420 mg/kg/day GSK2983559 in minipigs, the PK stopping criteria are based on  $AUC_{(0-24)}$  and  $C_{max}$  values at 1/3rd of the NOAEL of 120 mg/kg/day GSK2983559 (GSK2668176  $AUC_{(0-24)}$  50.9  $\mu\text{g}\cdot\text{h}/\text{mL}$ ,  $C_{max}$  7.5  $\mu\text{g}/\text{mL}$ ).

The decision to proceed to the next dose level of GSK2983559 in each part of this study will be made by the DEC, based on safety, tolerability, and preliminary PK data obtained (through at least 24 hours post dose) with at least 4 participants having received active treatment (GSK2983559) at the current dose level. The actual doses to be administered may be adjusted based on safety, tolerability and preliminary PK data at previous dose levels; these dose adjustments may involve either an increase or a decrease in the planned dose, but will not exceed PK criteria. Planned doses may also be repeated.

It is planned that the predicted human mean GSK2668176  $AUC_{(0-24)}$  or  $C_{max}$  values **will not** exceed the mean GSK2668176  $AUC_{(0-24)}$  and  $C_{max}$  values observed at one third of the NOAEL in minipig (16.94  $\mu\text{g}\cdot\text{h}/\text{mL}$  and 2.5  $\mu\text{g}/\text{mL}$ , respectively). In addition, the predicted human maximum  $AUC_{(0-24)}$  or  $C_{max}$  values **will not** exceed the maximum observed  $AUC_{(0-24)}$  and  $C_{max}$  values at one third NOAEL (21.6  $\mu\text{g}\cdot\text{h}/\text{mL}$  and 3.25  $\mu\text{g}/\text{mL}$ ).

### 8.2. PK criteria for 5-ABT and NAc-5-ABT

The drug product contains an impurity (5-ABT) known to be mutagenic (with unknown carcinogenic potential) that is controlled in drug production to assure its level is below a Threshold of Toxicological Concern (TTC) per the ICH M7 guideline. However, because of a possibility for 5-ABT to be formed in the body, monitoring for 5-ABT (and its metabolite, NAc-5-ABT) in blood plasma will be undertaken with application of the

same TTC (120 µg), which translates to a plasma concentration of 3 ng/mL under the assumption that the mutagenic impurity distributes into a volume equal to total body water of 42L. Based on this information, if in any individual the Cmax of combined concentration of 5-ABT and NAc-5-ABT (in ng/mL equivalents 5-ABT/mL) is > 3 ng/mL, it will suggest the TTC level of 120 µg has been reached and further dose-escalation will be stopped. During dose escalation, progression to the next dose level will be guided by the criteria where the maximum predicted 5-ABT amount for the next dose will not exceed the TTC of 120 µg.

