Phototoxicity	
Non-clinical data:
 
There is a potential risk that GSK2983559 can lead to photosensitivity responses in some people.
 
In a ultraviolet/visible light (UV/VIS) spectrum for GSK2983559 (max abs [absorbance] 340 nm) and GSK2668176 (max abs 339 nm) in acetonitrile (ACN)/water showed an absorbance between 290-700 nm demonstrated a risk for potential phototoxicity effects.
	
Participant Selection:
 
 
• Participants must agree to avoid prolonged UV exposure to natural sunlight or tanning beds for the duration of the study.
 
• Participants should be advised to wear protective clothing (e.g., sun hat, long sleeves) covering exposed areas and use a broad spectrum ultraviolet A/ultraviolet B (UVA/UVB) sunscreen and lip balm (SPF ≥30) on exposed areas when outdoors for a minimum of 5 half-lives after receiving GSK2983559. Participants should also wear sunglasses which filter UVA and UVB rays for a minimum of 5 half-lives after receiving GSK2983559.
 
 
Participant Monitoring:
 
 
• Participants should be monitored for adverse effects potentially related to phototoxicity.
 

Potential Risk of Clinical Significance	Summary of Data/Rationale for Risk	Mitigation Strategy
Mutagenicity/ Genotoxicity	
Non-clinical data:
 
5-amino-benzothiazole (5-ABT), an impurity and acid degradant, is mutagenic in an in vitro Ames assay. It is unknown if GSK2983559 itself presents a genotoxic hazard to humans.
	
Participant Monitoring:
 
 
Plasma samples from FTIH will be analysed for 5ABT and N-acetyl 5ABT at each dose level. Dose escalation will be halted if in any individual the Cmax of combined concentration of 5-ABT and n-acetyl-5-amino benzothiazole (NAc-5-ABT) (in ng/mL equivalents 5-ABT) is > 3 ng/mL in either the standard or enteric capsule.
 

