#### **5.5.5. Assessment and control of 5-ABT**

5-amino-benzothiazole (5-ABT), an impurity in the GSK2983559 drug substance (3-6 parts per million (ppm) [m.2.1.S.3.2 Impurities in chemistry, manufacturing and controls (CMC) investigational medicinal product dossier (IMPD)], was found to be mutagenic in an in vitro Ames assay. In addition, 5-ABT was formed from GSK2668176 in bio relevant media (pH 6.5 and pH 8 in FaSSIF and FeSSIF conditions), suggesting that a theoretical risk exists for its formation at physiological pH. According to ICH M7 guidance for the assessment and control of deoxyribonucleic acid (DNA) reactive (mutagenic) impurities in pharmaceuticals to limit potential carcinogenic risk, 5-ABT is classified as a Class 2 hazard (i.e. known mutagen with unknown carcinogenic potential) and must be controlled at or below the Threshold of Toxicological Concern (TTC) of 120  $\mu\text{g}/\text{day}$  considering the duration of treatment of  $\leq 1$  month..

5-ABT is not predicted to be a metabolite, and has not been observed as a metabolite in in vitro hepatocyte or S9 incubations. Real time analysis of plasma samples from FTIH for 5-ABT and its metabolite N-acetyl 5-ABT will be performed to monitor exposure to 5-ABT in healthy volunteers.

Quantifiable concentrations of 5-ABT were observed below the stopping criteria (combined  $C_{max}$  of 5-ABT and NAc-5-ABT of 3 ng/mL) in 4 out of 8 subjects treated with GSK2983559 in Cohort 1 at the 100-mg dose level. The maximum observed 5-ABT concentration was 1.25 ng/mL. An enteric capsule [Hydroxypropylmethyl Cellulose Acetate Succinate (HPMCAS)] will be used starting in Cohort 2 and carry through to Cohort 6 to determine if this formulation will minimize the gastric conversion of drug substance to 5-ABT. The disintegration of an enteric capsule is pH dependent and is expected to avoid hydrolysis of the active pharmaceutical ingredient (API) to 5-ABT in the acidic environment of the stomach and release API in a higher pH environment in the proximal small intestine.

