### 8.3. Safety criteria

The Principal Investigator and the GSK Medical Monitor will review the following and study dosing **will be** stopped if any of these criteria is met:

- One (1) or more participants experience a serious adverse event (SAE) which has a reasonable possibility of relation to study drug.
- Two (2) or more participants experience a severe or clinically significant non-serious adverse event (based upon investigator judgment) which has a reasonable possibility of relation to study drug.
- Two (2) or more participants in a Part A cohort or 3 or more participants in a Part B cohort experience the same adverse event of moderate severity which has a reasonable possibility of relation to study drug.
- Consistent Common Terminology Criteria for Adverse Events (CTCAE) Nervous System adverse events of any grade occur across participants that have a reasonable possibility of relation to study drug.

If dosing is halted and if deemed acceptable by GSK internal safety review to proceed with or modify dose escalation to further characterize the safety profile, a formal request with appropriate data and substantial amendment will be submitted to Medicines and Healthcare Products Regulatory Agency (MHRA) for approval.

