## 9. DISCONTINUATION CRITERIA

### 9.1. Individual Safety Stopping Criteria

- If a participant experiences a serious or severe clinically significant AE that in the clinical judgement of the Investigator, after consultation with the Medical Monitor, is possibly, probably or definitely related to investigational product.
- The participant initiates treatment with any prohibited medications.
- The participant develops a serious opportunistic or atypical infection.
- If any of the liver chemistry stopping criteria or QTc stopping criteria are met.
- The participant experiences any signs of suicidal ideation or behaviour.

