### 9.3.1. Study Treatment Restart or Rechallenge

During part B, study treatment restart or rechallenge after liver chemistry stopping criteria are met by any participant in this study is not allowed.

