### 11.3.4. Interim Analyses

Dose escalation meetings will occur after each period in Part A and after the completion of 14 days dosing of each cohort in Part B. The decision to proceed to the next cohort and next dose strength to be studied, will be made by DEC based on assessment of safety (e.g., AEs, clinical laboratory results, vital signs and ECG) and plasma GSK2983559 pharmacokinetic and 5-ABT concentrations obtained in all participants at the prior dose level. Individual safety data (adverse events, laboratory safety tests, ECGs and vital

signs) will be reviewed. This study is double blind (sponsor open), where the participant, investigator and site staff will remain blinded to the treatment allocation. Sponsor open refers only to those members of the DEC.

Following completion of Cohort 1 (Part A) and before starting Cohort 2 (Part A), a GSK internal safety board (independent of DEC) will be reviewing the data.

A formal interim analysis may be performed during the study on completed cohorts in Part A of the study to aid internal decision making only. Only the DEC members will be unblinded. There will be no changes to the study design or planned number of participants in future cohorts as a result of this interim analysis. This analysis may include review of individual participant data, summaries, graphical presentations and/or statistical analysis.

The Reporting and Analysis Plan will describe the planned interim analysis in greater detail.

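### In Part B, a 5-ABT result above 3 ng/mL stops dose escalation, but no written rule requires action for the participant still being dosed

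*Protocol*

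**What the plan says.** **The 5-ABT rule.** Protocol 8.2 converts the 120 µg threshold of toxicological concern to 3 ng/mL in plasma. When any individual exceeds it, the level "has been reached and further dose-escalation will be stopped". The mutagenicity row of 3.3.1 matches: "Dose escalation will be halted if in any individual the" combined Cmax is above 3 ng/mL, in either capsule. Section 8.2 adds a forward-looking limit: the largest 5-ABT amount predicted for the next dose must stay within 120 µg.

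**Why it is monitored.** Section 5.5.5 records that 5-ABT is mutagenic in vitro and sets 120 µg/day as the ceiling for treatment of up to one month. It adds: "Real time analysis of plasma samples from FTIH for 5-ABT and its metabolite N-acetyl 5-ABT will be performed".

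**The rules that stop dosing.** Section 8.3 begins "The Principal Investigator and the GSK Medical Monitor will review the following and study dosing" and lists four triggers for stopping, all of them adverse events. Section 9.1 covers related serious or severe events, prohibited medication, infection and suicidality, and includes: "If any of the liver chemistry stopping criteria or QTc stopping criteria are met". Section 9.2 adds neurological findings. For the liver criteria, 9.3.1 goes further: "During part B, study treatment restart or rechallenge after liver chemistry stopping criteria are met by any participant in this study is not allowed". None of these sections mentions 5-ABT.

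**Timing in Part B.** Dosing lasts 14 days, with once-daily dosing planned and twice-daily possible (5.1). Two sentinels are dosed to steady state, and the other eight start after their safety results are reviewed. Whether 5-ABT is among those results is not stated. Dose escalation meetings come "after the completion of 14 days dosing of each cohort in Part B" (11.3.4). As scheduled, full PK profiles are taken on Days 1 and 14 only (Table 4), with mainly pre-dose samples between (Table 3), although 10.4.1 allows samples to be added.

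**The concern.** In Part A a participant takes one dose per period and the next step is a higher dose, so stopping escalation is a real response to a crossing. In Part B the same participant is due the same dose again the next day, and the only stated response does not reach that dose. The protocol writes individual stops where it intends them, as for liver chemistry and QTc, so the absence of 5-ABT from those lists is noticeable.

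The participants are healthy and gain no medical benefit, and the protocol itself treats the limit as one that must be kept. It pays for a real-time assay but does not say what a result above the limit requires for someone in mid-course. Stopping then depends on discretion. The investigator's discretion is weakened because 10.4.2 withholds potentially unblinding concentrations from the site.

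**Working it through.** **1. The protocol's threshold.** Inputs from 8.2: 120 µg and 42 L of body water. 120 / 42 = 2.86 ng/mL, which rounds to the stated 3 ng/mL. In reverse, 3 ng/mL × 42 L = 126 µg, which is 5% above 120 µg. By the protocol's own conversion, a participant above 3 ng/mL is already past the daily limit.

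**2. What each provision does for a Part B participant who has crossed.**

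| Protocol section | Effect |
|---|---|
| 8.2, 3.3.1 | Bars the next level up; the current level is unaffected |
| 8.2, predicted amount | Limits which dose is reached next; acts before dosing |
| 8.3 | Stops study dosing, for adverse events only |
| 9.1–9.4 | Stops the individual; no 5-ABT item |
| 7.2 | Daily dose not to exceed the Section 8 criteria by intention; argues against re-dosing but names no hold, person or timing |
| Appendix 3 | Criteria applied strictly, but refers back to Section 8 |
| 5.5.4 | Requires the anticipated exposure to be cleared in Part A first; does not name 5-ABT |
| 7.4 | Permits unblinded committee review when needed |
| 10 | Sends immediate safety concerns to the sponsor to decide whether the participant continues |
| 9.5 | Permits withdrawal at the investigator's discretion |
| 11.3.4 | Scheduled review after dosing has ended |

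Several rows limit the dose or allow action. None requires the participant to stop.

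**3. Doses remaining.** Once daily, after a Day 1 crossing: 14 − 1 = 13. If twice-daily dosing were adopted: 28 − 1 = 27. Both assume that nobody acts. Assay turnaround is not given, so take as an assumption that the Day 1 result is known before dosing on Day d. A stop then averts 15 − d once-daily doses, or 2 × (15 − d) twice-daily doses:

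| Result known before dosing on | Averted, once daily | Averted, twice daily |
|---|---|---|
| Day 2 | 13 | 26 |
| Day 4 | 11 | 22 |
| Day 7 | 8 | 16 |
| Scheduled meeting, after Day 14 | 0 | 0 |

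**4. Sentinel.** The remaining eight participants are allocated 7:1, so if the active sentinel crosses, seven further active participants have not yet started.

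**5. What Part A can show.** Each blinded Cohort 2 dose level was planned with 12 − 3 = 9 active participants (Table 6). If none of 9 crosses, the one-sided 95% upper limit for the individual crossing rate is 1 − 0.05^(1/9) = 0.283, or 28%. This is a coarse bound: it ignores how far below 3 ng/mL the measured values lie. It shows that a clean Part A level does not exclude a crossing in Part B, and it is not an estimate of the risk.

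**The case against.** The case for leaving the text alone is substantial.

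- Knowingly repeating a dose that took a participant over the limit is hard to square with 7.2. Section 10 directs a safety concern to a decision on that participant's treatment, and 7.4 lets the committee look at unblinded data between meetings.
- Section 3.3.1 lists plasma 5-ABT as participant monitoring for a named risk, so the sentinel review may already include it.
- The 8.2 limit on the predicted amount, the Part A clearance and the enteric capsule all lower the chance of a crossing. The highest reported 5-ABT was 1.25 ng/mL (100 mg, standard capsule), or 1.25 × 42 = 52.5 µg. After enteric doses of 200 and 400 mg (SAP 5.1), SAP 2.1 reports too few quantifiable 5-ABT and NAc-5-ABT values to summarise.
- The 3 ng/mL figure is a surrogate for an impurity limit. It is not an observed toxicity such as raised ALT, so leaving individual action to judgement is defensible.
- The Dose Escalation Charter is not in the documents and may hold the rule.

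Most of this stands. It makes inaction unlikely, which is why 13 doses is a ceiling, and it means nobody should infer that the protocol directs dosing to continue after a crossing; it is silent. The SAP remark does not establish that there were no crossings, but it is the later evidence and points to a low likelihood. The objections do not supply a rule: every provision cited limits the dose beforehand, permits action or requires discussion.

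A reader might also infer that one crossing should automatically halt the whole cohort. The documents do not support that. Evaluability in Part B means completing 14 days (5.2) and replacements go to the same dose level, so a sustained hold triggered by one marginal value could leave no evaluable participants.

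**Conclusion.** The gap is real and narrow. For a Part B participant whose combined Cmax exceeds 3 ng/mL, the protocol states only that escalation stops, requires no action on that participant's remaining doses, and schedules committee review for after they have been taken. The size is at most 13 once-daily doses after a Day 1 crossing, if nobody acts; how many a stop would avert depends on a turnaround that is not stated. How often a crossing would occur cannot be estimated from the documents.

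The conclusion is about the written rules and assumes that the charter and the study reference manual, neither of which is available, do not already contain the stop. It does not mean that anyone was over-exposed in Part B: the study ended during Cohort 2 of Part A (SAP 2.1) and Part B was never dosed. The change is recommended for any further use of this design.

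**What to change.** - **8.2 and 9.1:** a Part B participant with a combined Cmax above 3 ng/mL receives no further GSK2983559 at that dose level.
- **5.1:** name the sentinel's 5-ABT and NAc-5-ABT result among the data reviewed before the remaining eight participants start.
- **11.3.4:** real-time Part B 5-ABT results go to the unblinded committee members during dosing, within a stated turnaround. A crossing triggers a prompt ad hoc review that decides whether the rest of the cohort continues, reduces dose or stops.
- If the charter already says this, a cross-reference is enough.

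**Cost.** A few sentences; the assay is already planned in real time. Individual stops lose completers, but 5.2 needs 4 evaluable of 8 on active, so 8 − 4 = 4 could be stopped with the minimum kept. That allowance covers individual stops only: if the committee stops the level, the cohort may be lost. A stop seen at the site could also reveal active treatment. Having the unblinded members send a dosing instruction without the concentration limits this risk but does not remove it. Waiting for the sentinel assay may delay the rest of the cohort.

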### Amendment 01 24-JUL-2018

#### Overall Rationale for the Amendment:

As described in Section 5.5.5 and Section 8.2 of this protocol, plasma concentrations of the mutagenic substance 5-ABT and its metabolite NAc-5-ABT are being monitored throughout the study to ensure that participants remain below the threshold of toxicological concern (TTC) of <120 µg/day (for up to one month of dosing) as defined by the ICH M7 guidance. Following administration of a single dose of 100 mg GSK2983559 in Cohort 1 of Part A, quantifiable concentrations of 5-ABT were observed in 4 of the 8 subjects dosed with GSK2983559. The maximum observed 5-ABT concentration of 1.25 ng/mL was below the stopping criteria of 3 ng/mL. The presence of quantifiable concentrations of 5-ABT in plasma is believed to be due to hydrolysis of the drug substance to form 5-ABT in the acidic conditions of the stomach. It is also known that the drug product contains 5-ABT; however, this is being controlled to < 10 ppm in the current synthetic route and extraction procedure.

This amendment will change the formulation from a standard capsule (HPMC) to an enteric capsule (HPMCAS) to determine if an enteric formulation minimises the gastric conversion of drug substance to 5-ABT. The disintegration of an enteric capsule is pH dependent and is expected to avoid hydrolysis in the stomach and release active pharmaceutical ingredient (API) in the higher pH environment in the proximal small intestine. The 5-ABT stopping criteria are unchanged and continue with progression in to Cohort 2 and if controlled will carry through Cohort 6.

PK parameters AUC and Cmax for GSK2983559 and GSK2668176 increase approximately linearly with increasing doses. Draft preliminary review of blinded safety data indicate that there are no clinical significant safety concerns. No SAEs or deaths have been reported. Cohort 2 is planned to start with a 200 mg dose and escalate to the top predicted dose which values **will not** exceed the mean GSK2668176 AUC(0-24) and Cmax values observed at one third of the No Observable Effect Limit (NOAEL) in minipig. The sample size for Cohort 2 will be increased from 8 to 12 subjects to monitor for 5-ABT concentrations in more subjects and to ensure at least 8 active subjects progress to the food effect dosing in this cohort.

Section # and Name	Description of Change	Brief Rationale

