## Dosing

- Once-daily (QD) dosing is planned in Part B, but twice-daily dosing (BID) may be considered based upon the PK profile as well as the safety and tolerability observed in Part A.
- Sentinel dosing will be employed within each cohort. On Day 1, one participant will receive GSK2983559 and one participant will receive matched-placebo, both participants will be dosed to steady state (approximately Day 2 minimum based on PK predictions from Part A). Dosing in the remaining 8 participants in each cohort will occur after review of safety results from the initial 2 participants in a 7:1 ratio (GSK2983559: placebo).

The decision on the dose level of GSK2983559 to be administered in Cohort 3 will be made at a DEC meeting based on all safety, tolerability, and PK data accumulated from Part A of the study. The decision to proceed to the next single dose level will be made at a DEC meeting (see [Appendix 3: Study Governance Considerations](#)).

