### Dose selection for Part B

Part B (repeat dose) of the study will be initiated after completion of Part A. Dose selection will be based upon consideration of available safety, tolerability and PK data from Part A and/or preceding repeat dose cohorts in Part B. Based on the observed half-life of approximately 8 h GSK2668176 in humans, minimum accumulation is anticipated after BID dosing. The dose of GSK2983559, noted as X, is anticipated to provide 90% inhibition at Ctrough levels of GSK2668176 in 50% of the population and will be re-estimated based on the PK and PD data collected in the early doses in Part A. The initial

dose in Part B (Cohort 3, repeat dose) will be approximately half X. Dose escalation in the repeat dose part of the study will not exceed 2-fold between cohorts and will be driven by safety and PK stopping criteria (see Section 8). In addition, a dose will not be assessed as a repeat dose until the anticipated steady-state exposure ( $C_{max}$  and  $AUC_{(0-\tau)}$  on Day 14) for that dose have been evaluated and shown not to have met safety stopping criteria in the single dose portion of the study (Part A). Based on current PK predictions a dose of 200 mg BID dosing regimen is predicted to provide 90% inhibition in approximately 90% of subjects. Dose levels higher than this may be explored in order to evaluate dose response in future phase 2 dose ranging study provided that exposure levels for that dose has been previously evaluated in Part A of the study.

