## 7.2. Dose Modification

This protocol allows some alteration from the currently outlined dosing schedule, but the maximum total daily dose will not intentionally exceed the PK stopping criteria defined in Section 8. Currently, the highest planned dose is 600 mg/day of GSK2983559.

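### The 5-ABT limit is 120 µg per day, but Protocol Section 8.2 tests it per dose; under BID dosing in Part B the written tests could allow about 148 µg/day

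*Protocol*

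**What the plan says.** **The limit.** Protocol Section 5.5.5 says 5-ABT "must be controlled at or below the Threshold of Toxicological Concern (TTC) of 120" µg/day, for treatment of up to one month. The Amendment 01 rationale gives the same daily figure as the purpose of the plasma monitoring.

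**The tests.** Section 8.2 applies what it calls the same threshold, written as 120 µg without a time unit. It does so in two ways:

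- A peak test. The threshold becomes a "plasma concentration of 3 ng/mL under the assumption that the mutagenic impurity distributes into a volume equal to total body water of 42L". A combined 5-ABT and NAc-5-ABT Cmax above that value in any individual stops further escalation.
- A predictive test. The "maximum predicted 5-ABT amount for the next dose will not exceed the TTC of 120" µg.

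**The regimen.** Section 5.1 (Part B, Dosing) says "Once-daily (QD) dosing is planned in Part B, but twice-daily dosing (BID) may be considered". Under Dose selection for Part B, "a dose of 200 mg BID dosing regimen is predicted to provide 90% inhibition in approximately 90% of subjects".

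**Related rules.** Section 7.2 says "the maximum total daily dose will not intentionally exceed the PK stopping criteria defined in Section 8". Dose selection for Part B adds that "a dose will not be assessed as a repeat dose until the anticipated steady-state exposure" (Cmax and AUC(0-τ) on Day 14) has been covered in Part A without meeting the stopping criteria. Section 5.5.4 plans a 400 mg single dose because 200 mg BID is the anticipated efficacious dose.

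**The concern.** A peak concentration and a per-dose amount are adequate stand-ins for a daily limit when there is one dose a day. With two doses a day, each can satisfy both tests while the daily sum exceeds the limit.

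This is the plan's quantitative control on 5-ABT formed in the bodies of healthy volunteers. Two nearby rules look as if they might supply the missing daily sum, but neither does:

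- Section 7.2 points the total daily dose to Section 8, and Section 8 contains no daily 5-ABT quantity. Its one 24-hour measure, AUC(0-24) in Section 8.1, is for GSK2668176.
- The Part B coverage condition uses per-interval measures of drug exposure, not a daily amount of impurity.

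**Working it through.** **Inputs.** Limit 120 µg/day (Section 5.5.5). Volume 42 L and trigger 3 ng/mL (Section 8.2). Absorption rate constant ka 0.85/h, predicted for GSK2668176 (Section 5.5.1). Observed GSK2668176 half-life about 8 h (Dose selection for Part B). BID interval τ = 12 h. No elimination data are given for 5-ABT or NAc-5-ABT.

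**1. The plan's own figure.** 120 µg / 42 L = 2.86 ng/mL, which rounds to 3. It reproduces. (Taken literally, 3 × 42 = 126 µg.)

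**2. Section 8.2 alone.** Two doses at the predictive cap give 2 × 120 = 240 µg/day. This is an outer limit. If a fraction f of combined 5-ABT remains after 12 h, the steady-state peak is 2.86/(1 − f). It stays at or below 3 only if f ≤ 1 − 2.86/3 = 0.048, a half-life below about 2.7 h.

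**3. Adding the Part B coverage condition.** Let R be the BID steady-state Cmax of GSK2668176 divided by its single-dose Cmax. A BID dose D then needs a Part A single dose of at least R × D. If the largest single dose that passes carries 120 µg, each BID dose carries 120/R and the day carries 240/R.

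For one compartment with first-order absorption, C(t) is proportional to ka/(ka − k) × [a·exp(−kt) − b·exp(−ka·t)]. At steady state a = 1/(1 − exp(−kτ)) and b = 1/(1 − exp(−ka·τ)). After a single dose a = b = 1.

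- k = ln 2 / 8 = 0.0866/h
- Single-dose peak: 0.772, at 2.99 h
- Steady-state peak (a = 1.547, b = 1.000): 1.254, at 2.42 h
- R = 1.254/0.772 = 1.625
- Per dose: 120/1.625 = 73.8 µg
- Per day: 240/1.625 = 147.7 µg, and 147.7/120 = 1.23 times the limit

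The AUC(0-τ) half of the condition is weaker. At steady state AUC(0-τ) equals the single-dose AUC(0-∞) of the same dose, so Cmax governs.

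**4. Sensitivity to ka.** At 8 h, ka = 0.4/h gives R = 1.741 and 138 µg/day; ka = 2/h gives R = 1.578 and 152 µg/day. With ka at 0.85/h, the excess disappears only when R reaches 2, at a half-life of about 11.1 h.

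**5. Would the 3 ng/mL peak test catch it?** Each dose adds 73.8/42 = 1.76 ng/mL. The steady-state peak 1.76/(1 − f) exceeds 3 only if f > 1 − 1.76/3 = 0.414. That needs a combined 5-ABT half-life above 12 × ln 2 / ln(1/0.414) = 9.4 h. Below that, both Section 8.2 tests pass.

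**6. Does Section 8.1 bind first?** On Table 7's linear scaling, the mean AUC(0-24) limit corresponds to 16.94/2.476 × 100 = 684 mg in a day. Step 3 therefore needs the 5-ABT cap to stop the total daily dose below roughly that.

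**The case against.** **The text can be read as daily.** Section 8.2 invokes the same threshold, defined elsewhere per day. Section 7.2 speaks of total daily dose. The words on the next dose sit in a sentence about moving to the next dose level. This is a fair reading of the predictive test. It does not repair the peak test, which cannot sum two doses, and a mutagen limit should not rest on an implied unit.

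**The named regimen is covered.** This largely stands. If 400 mg passes Section 8.2 as a single dose, 200 mg BID carries the same daily amount. But Section 5.5.4 plans that dose for drug exposure. It is not a 5-ABT rule and does not bind other BID doses.

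**Monitoring would help.** Sentinels are dosed to steady state first, samples are assayed in real time, and Day 1 and Day 14 sampling runs past a second daily dose. The committee would therefore see peaks after both doses, but only once dosing has begun, and no daily total is calculated. The written action in Section 8.2 is to stop further escalation.

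**Stronger readings the documents do not support.**

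- A reader might use the predicted 4.6 h half-life (Section 5.5.1), which gives R = 1.243 and 193 µg/day. The amended protocol reports about 8 h observed, which supersedes it.
- A reader might scale the 1.25 ng/mL seen at 100 mg to particular Part B doses. That value came from the standard capsule. Part B was to use the enteric capsule, introduced to reduce 5-ABT formation.
- A reader might call the 3 ng/mL figure miscalculated. It is not; what is missing is the time unit.

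**Conclusion.** The gap is real and should be fixed. A daily limit is enforced by two per-dose tests, BID is permitted, and no other rule sums 5-ABT over 24 hours.

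The supportable size is about 148 µg/day (138 to 152 for ka from 0.4 to 2/h), or 1.23 times the limit, with 240 µg/day as the outer bound from Section 8.2 alone. The 148 figure rests on four conditions:

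- the GSK2668176 half-life is about 8 h;
- 5-ABT amount is proportional to dose;
- the 5-ABT cap, not Section 8.1, limits the dose;
- the combined 5-ABT half-life is below about 9.4 h. Above that, the peak test would flag the regimen, but only after dosing.

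The last condition cannot be checked from the documents, so the figure is conditional.

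A reader might infer that participants were over-exposed. They were not exposed under this rule at all: SAP Sections 2.1 and 2.3 record termination during Cohort 2 of Part A, before Part B began. Once-daily dosing is unaffected.

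**What to change.** In Section 8.2, state the 120 µg as a 24-hour total. For BID dosing, require one of two things:

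- predicted 5-ABT of at most 60 µg per administration, which is 60/42 = about 1.4 ng/mL before accumulation; or
- that the total daily dose has already passed Section 8.2 as a Part A single dose, which makes the 400 mg plan for 200 mg BID a general rule.

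Section 7.2 then works as written, because Section 8 would hold a daily 5-ABT quantity for it to point to.

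The cost is a sentence or two of text and possibly a lower maximum BID dose. Where the bound above would have applied, the allowed amount per dose falls from 73.8 to 60 µg, so the dose falls by about 19% (1 − 60/73.8). Where 5-ABT is not the limiting criterion, the change may cost nothing.
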